Study Protocol with Statistical Analysis Plan

Title:

Evaluation of IL-2, IL-5, and IL-17 Levels in the Saliva of Patients Treated with Stainless Steel Crowns

NCT Number: NCT06439095

Date: May 1,2025

This prospective before-and-after clinical study was approved by the Local Ethics Committee of Van Yüzüncü Yıl University in accordance with the Declaration of Helsinki (Approval No: 2024/01-03). The study protocol was registered on ClinicalTrials.gov (NCT06439095). All parents/guardians were informed about the procedures and potential outcomes and were asked to sign a written informed consent form prior to participation. Children whose parents declined consent were excluded from the study.

Selection of Participants

Participants were selected among 30 patients who applied to the Pediatric Dentistry Clinic of Van Yüzüncü Yıl University Faculty of Dentistry. The study was conducted on 20 observations from 10 pediatric patients undergoing general anesthesia. Data were collected at two time points: baseline (before treatment) and seven days after treatment. All treatment plans followed routine pediatric dental protocols, and no modifications were made for study purposes. Therefore, the study posed no harm to the patients.

Inclusion criteria:

- Children aged 3–10 years
- Voluntary participation
- Clinical indication for stainless steel crowns (SSC) without need for additional crowns in the next month
- Adequate unstimulated saliva volume in the morning
- No need for space maintainers in the following month
- Candidates for treatment under general anesthesia

Exclusion criteria:

- History of previous dental treatment
- History of systemic disease or syndromes
- History of allergic reactions
- History of using imitation jewelry
- Presence of metal restorations or orthodontic appliances
- Patients not undergoing general anesthesia

This was a pilot/exploratory study, and no formal sample size calculation was performed. As no previous studies were available evaluating IL-2, IL-5, and IL-17 gene expression after SSC placement, the primary aim was to obtain preliminary data and provide a basis for future large-scale research.

Study Design

The study was performed under general anesthesia in children with material loss requiring SSC treatment. Patients were selected among those needing at least four posterior SSCs. To avoid delays and ensure no new SSC needs arose during the study period, all treatments were completed in a single session following standard pediatric protocols. Of 30 children evaluated, 12 met inclusion criteria and were enrolled.

Only patients receiving SSC or SSC combined with composite restorations were included. Those receiving other metal restorations, such as amalgam or space maintainers, were excluded.

Dental Treatments

The proximal surfaces of the teeth planned for SSCs were contoured with a #69L round bur on a high-speed handpiece. Occlusal surfaces were reduced by ~1 mm. Caries removal was performed using a round bur on a low-speed handpiece. In case of pulp exposure, an access cavity was prepared with an 008 fissure bur, and appropriate pulp therapy was conducted. SSCs (Kids Crown, Shinhung, Korea) were selected and cemented with nickel- and chromium-free glass ionomer cement (Meron, Voco, Germany).

Saliva Sampling

Saliva samples were collected at two time points: before treatment (control) and seven days after treatment. Parents were advised to follow a low-nickel diet and avoid nickel-containing materials until saliva collection was completed. The diet excluded canned foods, acidic foods cooked in stainless steel, herring, oysters, asparagus, beans, mushrooms, onions, corn, spinach, tomatoes, peas, whole grain flour, pears, rhubarb, tea, cocoa, chocolate, and baking powder. The use of fluoride-containing mouth rinses was also prohibited. Approximately 5 mL of unstimulated saliva was collected into polyethylene tubes free of nickel/chromium, washed with acetone and distilled water. Saliva was collected in the morning before surgery and at follow-up, without prior rinsing.

Clinical Examination

At follow-up, a pediatric dentist examined the oral mucosa and soft tissues for signs of allergic reactions, inflammation, or tissue changes using a dental mirror and light. Parents and children were asked about any discomfort or changes over the previous seven days.

RNA Isolation

Tissue samples were carefully collected with a sterile spatula, weighed at 25 mg, and placed in RNase-free tubes with 700 μ L TRIzol reagent. Samples were homogenized, incubated at room temperature for 5 minutes, mixed with chloroform, and centrifuged at 12,000 \times g, 4°C for 15 minutes. The upper phase was transferred, mixed with isopropanol, incubated, and centrifuged. The RNA pellet was washed with 75% ethanol, centrifuged, and air-dried. Pellets were dissolved in RNase-free water or buffer.

cDNA Synthesis

cDNA synthesis was performed on a cold plate at +4°C using the All-in-One cDNA synthesis kit (Solver). 1 μ L of RNA (10 ng/ μ L) was used in a 20 μ L reaction, incubated at 42°C for 60 minutes and 80°C for 10 minutes.

Gene Expression Analysis

cDNA products were analyzed using RotorGene Q. β -actin was used as the reference gene, and primers were designed for IL-2, IL-5, and IL-17. The PCR mixture included 12 μ L SYBR Green qPCR Master Mix, 2 μ L forward primer, 2 μ L reverse primer, 5 μ L water, and 4 μ L cDNA

(total volume 25 μ L). PCR cycling conditions were: 95°C for 15 min, followed by 45 cycles of 95°C for 30 s and 60°C for 30 s.

Statistical Analysis Plan

CT values obtained from Real-Time PCR were normalized using the Bio-Q online bioinformatics tool. Gene expression levels were calculated using the $2^{-\Delta\Delta CT}$ method. Group differences were analyzed using one-way ANOVA, and the Tukey HSD post-hoc test was used to identify significant differences. ΔCT values were calculated by subtracting housekeeping gene CT values from target gene CT values, and expression differences between groups were visualized using bar graphs.

Key Results Summary

Patients included were aged 3–6 years. Of the 12 enrolled, two were excluded due to loss to follow-up, leaving six girls and four boys. IL-2, IL-5, and IL-17 gene expression changes were assessed. Control group expression levels were low and homogeneous; follow-up samples showed marked increases, particularly in IL-5 and IL-17. IL-2 expression increased slightly without statistical significance. IL-5 increased moderately and reached statistical significance ($p < 0.05$), while IL-17 showed a sixfold increase and the highest variability, also reaching statistical significance. Heatmap and Venn diagram analyses illustrated expression changes and potential interactions among the genes.

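### One-way ANOVA ignores the before/after pairing, and the IL-17 'sixfold' has no stated scale, calibrator, averaging method or confidence interval; analyse within-child ΔΔCT and report a geometric-mean fold with 95% CI

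*Combined protocol and SAP*

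**What the plan says.** On design, Selection of Participants states "The study was conducted on 20 observations from 10 pediatric patients undergoing general anesthesia". Saliva Sampling adds "Saliva samples were collected at two time points: before treatment (control) and seven days after treatment". The control values are therefore the same children's own pre-treatment samples.

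On analysis, the Statistical Analysis Plan first has CT values normalised with the Bio-Q online tool. It then says "Gene expression levels were calculated using the" 2^-ΔΔCT method, followed by "Group differences were analyzed using one-way ANOVA, and the Tukey HSD post-hoc test was used to identify significant differences". Next it defines a second quantity: ΔCT "values were calculated by subtracting housekeeping gene CT values from target gene CT values". Neither quantity is tied to the ANOVA. The calibrator for ΔΔCT, the averaging of folds and any confidence interval are not mentioned.

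On results, the Key Results Summary reports "Control group expression levels were low and homogeneous; follow-up samples showed marked increases, particularly in IL-5 and IL-17", and that "IL-17 showed a sixfold increase and the highest variability, also reaching statistical significance". It gives no SD, CT value or interval.

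On purpose, Selection of Participants says that "the primary aim was to obtain preliminary data and provide a basis for future large-scale research".

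**The concern.** There are two linked problems.

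- **Pairing.** One-way ANOVA treats the 10 baseline and 10 follow-up values as independent. If a child's two values are positively correlated, the ANOVA error term is too large for the comparison, and the test becomes conservative and loses power. Tukey HSD adds nothing to a comparison of two time points, and the plan defines no further groups.
- **Meaning of the estimate.** CT is a log2 scale and fold is its exponential. An arithmetic mean of folds is pulled up by the largest values; a geometric mean is not. The gap grows with variability, and IL-17 is the gene described as most variable.

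The IL-17 fold is the only numerical effect size in the document, and the study exists to inform larger ones. A later team would pick up that figure without knowing which average it is or how precise it is.

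**Working it through.** **What can be reproduced.** Only the counts: 12 enrolled − 2 lost = 10 children, and 10 × 2 = 20 observations. 'Sixfold' cannot be reproduced, because no CT values or SDs are given.

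**Assumptions.** Log2 expression is bivariate normal; n = 10 pairs; two-sided 5% tests; ANOVA is run per gene on two groups (18 df). The SDs (0.5 to 2 cycles) and correlations (0 or 0.5) are assumed.

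**1. Cost of ignoring the pairing (ΔCT scale, equal SD σ at both times).** The variance of the mean difference is 2σ²(1−ρ)/n, but ANOVA uses 2σ²/n. At ρ = 0.5 the test statistic shrinks by √0.5 = 0.707, so the 18-df cut-off of 2.10 acts like 2.10/0.707 = 2.97. Simulation with 100,000 trials per scenario gives:

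| Scenario (ρ = 0.5) | Unpaired ANOVA on ΔCT | Paired t on ΔΔCT |
|---|---|---|
| No change, SD 0.5 to 2 | about 1% | 5% |
| True twofold rise, SD 1 | about 59% | 80% |

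At ρ = 0 pairing costs a little. For a true sixfold rise, power goes from 95% unpaired to 93% paired at SD 1.5, and from 78% to 73% at SD 2.

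**2. If 'sixfold' is an arithmetic mean of own-baseline folds.** With s the SD of ΔΔCT in cycles, the expected arithmetic/geometric ratio is exp((s·ln 2)²/2) = exp(0.2402·s²). The implied geometric fold is 6 divided by that ratio.

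**3. If 'sixfold' is already geometric.** The 95% CI is 6 divided and multiplied by 2^(2.262·s/√10).

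| s (cycles) | Arithmetic/geometric ratio | Geometric fold if 6 is arithmetic | CI factor | 95% CI if 6 is geometric |
|---|---|---|---|---|
| 0.5 | 1.06 | 5.7 | 1.28 | 4.7–7.7 |
| 1 | 1.27 | 4.7 | 1.64 | 3.7–9.9 |
| 1.5 | 1.72 | 3.5 | 2.10 | 2.9–12.6 |
| 2 | 2.61 | 2.3 | 2.70 | 2.2–16.2 |

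**4. If 'sixfold' is a ratio of arithmetic group means.** For a true geometric 6, the ratio of the population means is 6·exp((ln 2)²(s_f² − s_b²)/2), with s_b and s_f the baseline and follow-up SDs.

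- Equal SDs: the exponent is 0, so the ratio is 6; the simulated median at n = 10 is also 6.0.
- SDs 0.5 and 2: 6·exp(0.4805 × 3.75/2) = 6 × 2.46 = 14.8; the simulated median at n = 10 is about 12.
- SDs 1 and 2: 6·exp(0.4805 × 3/2) = 6 × 2.06 = 12.3; the simulated median is about 10.3.

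This average is therefore safe only if the spread is the same at both times. The results describe homogeneous controls and a highly variable IL-17, so equal spread cannot be taken for granted.

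**5. Does significance survive?** If 6 is geometric, a paired test gives p < 0.05 whenever 2.262·s/√10 < log2(6) = 2.585, that is, for s below 2.585 × 3.162/2.262 = 3.6 cycles.

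**The case against.** The study is declared a pilot without a sample size calculation, and a later planner would need an SD as well as a fold. Every figure above depends on SDs and correlations that the documents do not give. This stands: the figures show how large the problem could be, not how large it is. It does not remove the point, because a pilot's value lies in an interpretable estimate with an interval, and the plan specifies neither.

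Several stronger readings are tempting, but the documents do not support them:

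- *The ANOVA was run on folds.* Results worded as folds, with homogeneous controls and a highly variable sixfold gene, fit this. Testing ΔCT and reporting folds fits equally well.
- *The calibrator must be either own baseline or the control mean.* Calling the pre-treatment sample the control makes these likely, and an own-baseline calibrator would set every control to exactly 1. But normalisation went through Bio-Q, and a setting of that tool cannot be excluded.
- *Testing folds always loses power.* It does not. For a true twofold rise at SD 1 and correlation 0, own-baseline folds reject 57% of the time against 51% for the paired test. Part of that excess reflects their own false-positive rate of about 7–8%.
- *The test always rejects too rarely.* The 1% figure needs positive correlation and similar SDs. At SDs 0.5 and 2, unpaired ΔCT rejects about 6% under no change at correlation 0 and about 4% at correlation 0.5.
- *The ANOVA had two groups.* This is assumed. The groups are never defined, and Tukey HSD would be redundant with two. If the layout differed, the ANOVA figures above do not apply.

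**Conclusion.** The concern holds as a mismatch between test and design together with an undefined effect estimate. The mismatch can be read directly from the document: 10 within-child pairs are compared with a test for independent groups. With two groups per gene, equal SDs and correlation 0.5, this costs about 21 percentage points of power for a twofold rise at SD 1 (80 − 59).

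The gap in the estimate does not depend on which scale was tested. The IL-17 figure could be a geometric 6, or an arithmetic 6 that corresponds to a geometric value between 5.7 and 2.3 for ΔΔCT SDs of 0.5 to 2. Even a geometric 6 could have an interval as wide as 2.2–16.2 at SD 2.

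A reader might infer that the reported significance for IL-5 or IL-17 is wrong, or that 'sixfold' is overstated. The documents support neither inference: the first needs the CT data, and the second needs the averaging method.

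**What to change.** State which variable entered the ANOVA, which calibrator was used (including any Bio-Q setting) and how 'sixfold' was averaged. Then replace the ANOVA and Tukey sentence with wording such as:

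> For each gene, the within-child ΔΔCT (day 7 minus baseline ΔCT, log2 scale) is analysed by a paired t-test. The mean ΔΔCT and its 95% CI are back-transformed to a geometric-mean fold change, 2^-(mean ΔΔCT), with 95% CI.

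Restate the IL-17 result on that basis; it stays at 6 if it was already 2^-(mean ΔΔCT).

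The cost is a short re-analysis of existing CT values, with no new data. Reported folds may shrink, and borderline p-values may move in either direction. If the within-child correlation is near 0, the small loss of power against unpaired ΔCT shown in step 1 applies.

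### One-way ANOVA with Tukey HSD treats 10 before/after pairs as independent groups, so the reported p-values may be off in a direction the documents do not reveal

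*Combined protocol and SAP*

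**What the plan says.** The opening paragraph describes the design as "This prospective before-and-after clinical study". Under Selection of Participants, "The study was conducted on 20 observations from 10 pediatric patients undergoing general anesthesia". The control is not a separate set of children. Under Saliva Sampling, "Saliva samples were collected at two time points: before treatment (control) and seven days after treatment".

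For the analysis, the Statistical Analysis Plan section says: "Group differences were analyzed using one-way ANOVA, and the Tukey HSD post-hoc test was used to identify significant differences". No other test is named, and there is no mention of pairing, repeated measures or a child effect. The section also describes ΔCT values and 2^-ΔΔCT expression levels without saying which was tested. The Gene Expression Analysis section states that "β -actin was used as the reference gene", but the calibrator sample for ΔΔCT is not given.

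On purpose and size, Selection of Participants says "This was a pilot/exploratory study, and no formal sample size calculation was performed" and that "the primary aim was to obtain preliminary data and provide a basis for future large-scale research". The Key Results Summary nevertheless gives a significance verdict for each gene: IL-2 not significant, IL-5 significant (reported only as below 0.05), and IL-17 significant, with a sixfold rise and the largest spread.

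**The concern.** With one baseline and one day-7 sample per child, the relevant variance is that of the within-child difference. One-way ANOVA uses the within-group variance instead and counts error degrees of freedom as if every observation came from a different child. Tukey HSD adjusts for multiple comparisons and does not repair this.

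All three reported conclusions rest on this test. Without exact p-values, SDs or individual values, a reader can neither check them nor convert them to a paired result.

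The study's own aim is also affected. A larger before/after study would need the mean within-child difference, its SD and its confidence interval, and the plan produces none of them.

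**Working it through.** **Inputs from the document.** 12 enrolled - 2 lost = 10 children; 10 × 2 time points = 20 observations. The plan has no sample size, power or alpha calculation to reproduce.

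**Assumptions.** Two-sided 5%. The within-child correlation r and the ratio k of day-7 SD to baseline SD are not reported, so both are varied. The plan does not define the ANOVA groups; the layouts below are examples and do not bound the possibilities.

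**A. One before/after ANOVA per gene, on ΔCT, common calibrator, normal data.** Error df = 20 - 2 = 18, critical |t| = 2.101. With two groups the Tukey critical value is the same, so Tukey adds nothing. The paired t-test has 9 df and critical |t| = 2.262. Within any dataset,

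t_paired = t_unpaired × √[(1 + k²)/(1 + k² - 2rk)].

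True type I error of the ANOVA (numerical integration, checked by simulation):

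| k | r = -0.3 | 0 | 0.3 | 0.5 | 0.7 |
|---|---|---|---|---|---|
| 1 | 8.3% | 5.0% | 2.3% | 0.95% | 0.2% |
| 2 | 8.2% | 5.5% | 3.1% | 1.8% | 0.9% |
| 3 | 7.9% | 5.9% | 4.0% | 2.9% | 2.0% |
| 5 | 7.5% | 6.2% | 5.0% | 4.2% | 3.5% |

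In simulation the paired t-test stays at about 5% throughout.

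Power, ANOVA vs paired t, for an assumed shift of one root-mean-square SD:

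| k | r = 0 | 0.3 | 0.5 | 0.7 |
|---|---|---|---|---|
| 1 | 56% vs 51% | 57% vs 66% | 59% vs 80% | 61% vs 95% |
| 5 | 57% vs 51% | 57% vs 56% | 58% vs 60% | 58% vs 65% |

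The two tests reach their 5% thresholds together at r = [1 - (2.101/2.262)²] × (1 + k²)/(2k), which is 0.14, 0.17, 0.23 and 0.36 for k = 1, 2, 3 and 5. A paired p of 0.05 corresponds to an ANOVA p of 0.036 at r = 0. At r = 0.5 it corresponds to 0.127, 0.097, 0.075 and 0.057 for the same four values of k.

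**B. As A, but on fold values.** With equal ΔCT SDs of 0.5, 1 and 2 cycles (assumed), type I error is 4.8%, 4.1% and 2.6% at r = 0, and 1.0%, 0.9% and 0.7% at r = 0.5.

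**C. One ANOVA per gene, each child's own baseline as calibrator.** The control values are then constant. With s the SD of the follow-up values, the error mean square is s²/2 and the standard error is √(2 × s²/2 / 10) = s/√10. The t statistic therefore equals the paired one but is referred to 18 df instead of 9: P(|t₉| > 2.101) = 6.5% for normal values, whatever r is. For raw fold values it is about 7% to 8%.

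**D. One pooled ANOVA of control plus three genes, own-baseline calibrator.** Error df = 40 - 4 = 36, Tukey critical |t| = 2.69. For gene g with variance v_g, the squared standard error relative to the paired one is (v₂ + v₅ + v₁₇)/(2v_g).

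- Type I error per gene (independent normal genes): about 0.3% with equal SDs; about 0%, 0.04% and 4.5% with SDs 1, 2 and 4.
- Upper limit for the most variable gene, when the others have negligible spread: P(|t₉| > 2.693/√2) = 8.9%.
- Power for a gene shifted by 1 SD of its own difference: 80% paired, 46% pooled with equal SDs, and 12% pooled with SDs 1, 1 and 2 when the gene has SD 1.

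**The case against.** The strongest reply is that the practical consequence is unproven. If the test was a two-group comparison on ΔCT with a common calibrator, similar SDs and positive correlation, the ANOVA is conservative: the significant IL-5 and IL-17 results would stand and only the IL-2 verdict would be in doubt. If day-7 values are much more variable than baseline, the distortion is modest: at k = 5 the error runs from 3.5% to 7.5% over the correlations shown. The results summary describes homogeneous controls and a highly variable IL-17, which is compatible with a large ratio. The study is also labelled exploratory.

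This limits what can be claimed, but the document does not establish the benign conditions, and layout C or a negative correlation reverses the direction. The exploratory label explains the missing sample size calculation; it does not make an independent-groups test suit paired data, and significance is reported all the same.

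Three narrower points also stand:

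- A six-group layout (three genes by two times, 54 error df, Tukey critical |t| about 2.95) fits the text as well. It ignores pairing too.
- In layout C, pairing alone makes any result less significant, but only on an unchanged scale. If folds were tested and the re-run uses ΔCT, results can move either way. With SD 2 and a shift of 2 cycles (assumed), about 29% of simulated datasets become significant and 6% cease to be. With SD 1 and shift 0.5, the figures are 2% and 15%.
- Choosing ΔCT is a further analytic decision that does not follow from pairing alone, and the correction should say so.

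**Conclusion.** The concern holds, with high confidence, and the analysis must be corrected. The mismatch between design and test is plain in the text and does not depend on any assumed figure. Its effect does: across the illustrative layouts the true error of a nominal 5% comparison runs from near zero to almost 9%, and the loss of power from none to severe.

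The IL-5 and IL-17 findings are not shown to be wrong. The IL-2 verdict is the most exposed under A if the correlation is positive enough to pass the break-even values. Under D a real IL-2 change could be missed because IL-17's spread enters its error term. Under C, on a fixed scale, pairing would make IL-2 less significant. Which of these applies cannot be determined from the document.

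**What to change.** Issue a dated addendum to the Statistical Analysis Plan. Keep the record that ANOVA with Tukey HSD was used, and state that the correction was made after the results were known. Suggested text:

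> For each gene, the within-child difference in ΔCT (day 7 minus baseline) is analysed with a two-sided paired t-test on 10 pairs, reporting the mean difference, its SD and 95% CI, the back-transformed fold change and the exact p-value.

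State the calibrator sample, the scale and the groups used in the reported ANOVA. Re-run the three comparisons and restate the IL-2, IL-5 and IL-17 results from them as exploratory. A signed-rank sensitivity analysis and Holm-adjusted p-values are optional.

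The cost is an addendum and a re-run on data already held. Error df fall from 18 to 9. If the correlation is near zero and SDs are equal, power for a 1-SD shift drops from 56% to 51% and the interval is about 8% wider (2.262/2.101 = 1.077). The restated results may differ from those already summarised.

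### The SAP analyses 10 children measured twice with a one-way ANOVA and specifies no pairing by child, no SD of within-child change and no confidence interval

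*Combined protocol and SAP*

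**What the plan says.** All places are in the combined protocol and SAP.

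- **Design and size** (Selection of Participants): "The study was conducted on 20 observations from 10 pediatric patients undergoing general anesthesia".
- **What the control is** (Saliva Sampling): "Saliva samples were collected at two time points: before treatment (control) and seven days after treatment". The control is therefore the same children at an earlier time, not a separate group.
- **Purpose** (Selection of Participants): "This was a pilot/exploratory study, and no formal sample size calculation was performed"; "the primary aim was to obtain preliminary data and provide a basis for future large-scale research".
- **Analysis** (Statistical Analysis Plan): CT values are normalised and expression is computed by 2^-ΔΔCT. Then: "Group differences were analyzed using one-way ANOVA, and the Tukey HSD post-hoc test was used to identify significant differences". On the scale, ΔCT "values were calculated by subtracting housekeeping gene CT values from target gene CT values". On presentation, "expression differences between groups were visualized using bar graphs".
- **Results** (Key Results Summary): "Control group expression levels were low and homogeneous". IL-5 and IL-17 are called statistically significant and IL-2 is not. IL-17 is given as a sixfold increase with the largest variability. No SD or interval appears.

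The Statistical Analysis Plan does not define the ANOVA groups, the calibrator for ΔΔCT, or whether the test was run on ΔCT or on fold values.

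**The concern.** Two samples from one child are likely to be related. A one-way ANOVA has no term for the child, so it takes the 20 values as independent. Its standard error is then wrong whenever the within-child correlation is not zero: too large if the correlation is positive, too small if it is negative. The p-values carry that error.

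The output also leaves out what a reader of a small before-and-after pilot most needs: the size of the change in a child, how much it varies between children, and how precisely 10 pairs estimate it. A later paired study would be sized from the SD of within-child change. Neither the ANOVA residual SD nor an error bar at each time point gives that SD, because it also depends on the correlation, which the SAP does not ask for.

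**Working it through.** **1. The plan's own count.** Study Design gives 12 enrolled and Key Results Summary gives two lost to follow-up. 12 - 2 = 10 children; 10 × 2 time points = 20 observations. This matches the stated figure. No sample size or power formula is stated, so there is none to reproduce.

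**2. What the ANOVA amounts to.** Assume one ANOVA per gene comparing the two time points, 10 values each.
- Degrees of freedom are 1 and 18. The critical F at 5% is 4.414 = 2.101², and t(0.975; 18) = 2.101.
- Tukey HSD for two groups, q/√2 at 18 df, is also 2.101.

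So the ANOVA is an unpaired t-test and Tukey adds nothing.

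**3. Effect of ignoring the pairing.** With SD σ at each time point and within-child correlation ρ, the mean change over n children has true variance 2σ²(1-ρ)/n. The unpaired test uses 2σ²/n. Its standard error is therefore 1/√(1-ρ) times the true one. The error rates below come from simulation: n = 10, bivariate normal, equal SDs, two-sided 5%, 200,000 runs for each ρ. The documents give no correlation, so every ρ is an assumption.

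| ρ | SE used / true SE | Type I, unpaired | Type I, paired | Power at 1 SD, unpaired | Power at 1 SD, paired |
|---|---|---|---|---|---|
| -0.3 | 0.88 | 8.2% | 4.9% | 56% | 42% |
| 0 | 1.00 | 5.0% | 5.0% | 56% | 51% |
| 0.3 | 1.20 | 2.3% | 4.9% | 57% | 66% |
| 0.5 | 1.41 | 0.9% | 4.9% | 59% | 80% |
| 0.7 | 1.83 | 0.2% | 5.0% | 60% | 95% |

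**4. What a confidence interval would show.** The half-width for mean change is t(0.975; 9) × SD/√10 = 2.262 × SD/3.162 = 0.715 × SD cycles. Read the sixfold IL-17 figure as a geometric mean: log2(6) = 2.585 cycles. For assumed SDs of change:
- SD 1: 2.585 ± 0.715 cycles, or 3.7- to 9.9-fold.
- SD 2: 2.585 ± 1.431 cycles, or 2.2- to 16.2-fold.
- SD 3: 2.585 ± 2.146 cycles, or 1.4- to 26.6-fold.

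The one reported number fits all three.

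**5. What the SD of change is worth for planning.** SD of change = σ√(2(1-ρ)). Take a later paired study, a twofold target change (1 cycle), two-sided 5%, 80% power (noncentral t) and an assumed σ of 2 cycles:
- ρ = 0, 0.3, 0.5 and 0.7 give an SD of change of 2.83, 2.37, 2.00 and 1.55 cycles, and 65, 46, 34 and 21 pairs.

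Reporting the SD of change removes that dependence on ρ. Sampling error remains. The 95% limits for an SD on 9 df are √(9/19.02) = 0.69 and √(9/2.70) = 1.83 times the estimate. An estimate of 2 cycles has limits 1.38 and 3.65, so 34 pairs becomes 17 to 107.

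**The case against.** **A within-child change may already be computed.** ΔΔCT is a difference from a calibrator, and the calibrator is not stated. A reader might infer that the plan computes no within-child change at all. The text does not support that, because a per-child ΔΔCT cannot be excluded as a calculation step. What stands is that no such change is specified as the quantity summarised or tested. Nor would it rescue the ANOVA: with each child's own baseline as calibrator, every control value on the fold scale would be 1 by construction, and comparing groups by ANOVA would not be valid.

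**The significance labels may be right.** A reader might infer that the IL-5 and IL-17 labels are false. The documents do not show this. With positive correlation the unpaired test is conservative, so a paired test could support them more strongly. The type I error exceeds 5% only at negative correlation.

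**It is a declared pilot, and its aim is broad.** This stands in part. Pilot status explains the missing sample size calculation, which is not criticised here. The documents do not say that the later study will be paired or that this one must supply its sample size; direction of change and choice of gene are also a basis for further work. The planning argument therefore holds only for a paired follow-up. Nor does the SD of change settle the size of that study: the range of 17 to 107 pairs is wider than the 21 to 65 that comes from the unknown correlation, although the latter treats the time-point SD as known.

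**The results are only a short summary.** Missing SDs there do not prove that none were calculated, and the remarks on homogeneity and variability suggest that spread was looked at. The gap is in the Statistical Analysis Plan.

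**Conclusion.** The point holds as a defect of the planned analysis. The design is paired, and the SAP specifies neither a paired test nor a paired estimate with its precision. If the ANOVA compares the two time points gene by gene, its true type I error lies between about 8.2% and 0.2% over assumed correlations from -0.3 to 0.7. At 0.5 it has about 59% power for a 1-SD shift, where the paired test has 80%. These figures assume normal values with equal SDs and 10 complete pairs. If the groups were instead defined by gene and time, the equivalence to a t-test and these error rates would not apply as given, but the child would still be left out.

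The direction of the error in this study is unknown because no correlation is reported. No reported result is shown to be wrong. The change should be made because the paired estimate is a better method for this design.

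**What to change.** For each gene, replace the one-way ANOVA and Tukey HSD with a paired analysis of ΔCT, day 7 minus baseline, using all evaluable linked pairs. Report:

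- the number of pairs (the documents do not state that all 10 are evaluable for every gene);
- the mean change in ΔCT with 95% CI;
- the geometric-mean fold change, 2 to the power of minus that mean, with 95% CI;
- the SD of within-child change with its own 95% CI;
- the paired p-value.

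State the ΔΔCT calibrator, what the ANOVA groups were, and the scale on which the ANOVA was run. Because results are already known, the paired analysis cannot now be prespecified. Label it post hoc and exploratory and show it beside the reported ANOVA, so that a reader can see whether any conclusion depends on the choice.

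Cost: SAP wording, a little more analysis and a few table columns from ΔCT values already obtained, provided the samples can be linked by child. No new samples are needed. The downside is that the results may read as less definite, and that the SD of change supports planning only together with its CI.
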